This amendment is considered to be non-substantial based on the criteria set forth in Directive 2001/20/EC because it neither significantly impacts the safety or rights of participants or on the reliability and robustness of the data generated in the clinical trial.

Overall Rationale for the Amendment:

Protocol updated to clarify study procedures, as well as the inclusion of minor additions/updates to comply with protocol template guidance.

Summary change table from previous version of the protocol

Any new or amended text in the protocol is indicated in bold (IS column). Deletions are marked in strikeout text (WAS column). Minor formatting and editing are not included.

Section	WAS (Version 2.0, 13 SEPTEMBER 2022)	IS (Version 3.0, 04 DECEMBER 2023)	Rationale
Sponsor Signatory	
Sponsor Signatory: PPD
 
Medical Monitor Name and Contact Information: PPD
	
Sponsor Signatory: PPD
 
Medical Monitor Name and Contact Information: PPD
	Change in sponsor personnel

Section	WAS (Version 2.0, 13 SEPTEMBER 2022)	IS (Version 3.0, 04 DECEMBER 2023)	Rationale
	PPD Ipsen Bioscience, Inc. [name] United States Email: PPD	PPD Ipsen Bioscience, Inc. [name] United States Email: PPD	
7.1.1 Temporary Discontinuation	In case of suspected or confirmed COVID-19 (SARS-CoV-2) infection , the intervention administration may be temporarily postponed depending on the participant clinical presentation.	In case of clinical study disruption due to a regional or national emergency declared by a government agency , the intervention administration may be temporarily postponed depending on the participant clinical presentation.	Minor additions/updates to comply with protocol template guidance.
7.3 Lost to Follow-up	A participant will be considered lost to follow-up if he repeatedly fails to return for scheduled visits and is unable to be contacted by the study site. (...) 
 Should the participant continue to be unreachable, he will be considered to have withdrawn from the study. Site personnel will attempt to collect the vital status of the participant within legal and ethical boundaries for all participants randomised, including those who did not receive study intervention. Public sources may be searched for vital status information. If vital status is determined as deceased, this will be documented, and the participant will not be considered lost to follow-up. Sponsor personnel will not be involved in any attempts to collect vital status information. 	A participant will be considered lost to follow-up if the participant repeatedly fails to return for scheduled visits and is unable to be contacted by the study site until the end of the study . (...) 
 Should the participant continue to be unreachable, attempts to make contact should continue until study closure and participant might be confirmed as lost to follow up at the time of study closure. Site personnel will attempt to collect the vital status of the participant within legal and ethical boundaries for all participants randomised, including those who did not receive study intervention. All sources may be searched for vital status information. If vital status is determined as deceased, this will be documented, and the participant will not be 	Minor additions/updates to comply with protocol template guidance.

Section	WAS (Version 2.0, 13 SEPTEMBER 2022)	IS (Version 3.0, 04 DECEMBER 2023)	Rationale
		considered lost to follow-up. Sponsor personnel will not be involved in any attempts to collect vital status information.	
Section 8 Study Assessments and Procedures	
 Immediate safety concerns should be discussed with the sponsor immediately upon occurrence or awareness to determine if the participant should continue or discontinue study intervention. 	
(...)
 
• In the event of a significant study-continuity issue (e.g. caused by a pandemic), alternate strategies for participant visits, assessments, medication distribution and monitoring may be implemented by the sponsor or the investigator, as per local health authority/ethics requirements.
 
(...)
	Minor additions/updates to comply with protocol template guidance.
Section 8.4 Adverse Events and Serious Adverse Events and Other Safety Reporting	
AEs will be reported by the participant (or, when appropriate, by a caregiver, surrogate).
 
The investigator and any qualified designees are responsible for detecting, documenting, and recording events that meet the definition of an AE or SAE and remain responsible for following up all AEs and SAEs during the study (see Section 7).
	
The investigator and any qualified designees are responsible for detecting, documenting, and recording events that meet the definition of an AE or SAE and remain responsible for following up all AEs and SAEs during the study (see Section 7). This includes events reported by the participant (or, when appropriate, by a caregiver, surrogate, or the participant's legally authorised representative).
	Minor additions/updates to comply with protocol template guidance.
Section 8.4.5 Pregnancy	
(...)
 
• If a pregnancy is reported, the investigator will record pregnancy information on the appropriate forms (Pregnancy Notification Form—paper form) and submit it to the sponsor within 24 hours via email of learning of the female partner of male participant becoming pregnant (after obtaining the necessary signed informed consent from the female partner).
	
(...)
 
• If a pregnancy is reported, the investigator will record pregnancy information on the appropriate form and submit it to the sponsor within 24 hours via email of learning of the female partner of male participant becoming pregnant (after obtaining the necessary signed informed consent from the female partner).
 
• While pregnancy itself is not considered to be an AE or SAE, any pregnancy complication or elective termination of a
	Minor additions/updates to comply with protocol template guidance.

Section	WAS (Version 2.0, 13 SEPTEMBER 2022)	IS (Version 3.0, 04 DECEMBER 2023)	Rationale
	
 Any pregnancy complication or elective termination of a pregnancy for medical reasons will be reported as an AE or SAE. 	pregnancy for medical reasons will be reported as an AE or SAE.	
Section 8.4.8 Reporting of Study Intervention Errors Including Misuse/ abuse	
 Study intervention errors and uses outside of what is foreseen in the protocol will be recorded in the eCRF irrespective of whether associated with an AE/SAE or not. It will also be documented in the AE section of the eCRF if associated with an AE. It will be reported in the safety database only if associated with an SAE. 	
 Study intervention errors and uses outside of what is foreseen in the protocol, such as misuse, abuse or overdose, will be recorded on the appropriate eCRF page irrespective of whether associated with an AE/SAE or not, within 24 hours of investigator or qualified designees' awareness. If an AE/SAE is associated with this study intervention error, it should be documented in the AE/SAE section of the eCRF. Please refer to Sections 6.7 and 10.3.1. 	Minor additions/updates to comply with protocol template guidance.
Section 10.1.5 Dissemination of Clinical Study Data	
 The sponsor seeks to publish the results of its clinical trials in biomedical journals, whatever the outcome. Clinical trial results may also be presented at international congresses as posters or oral presentations. Protocol and result summary will be made publicly available on the United States Clinical Trials Registry (ClinicalTrials.gov) and for studies run in the EU/EEA on the EU Clinical Trials Register (www.clinicaltrialsregister.eu). The sponsor also provides clinical trial information to other national clinical trial registries or databases according to local requirements/legislation. 	
 Protocol information and final study result will be made publicly available on the United States website (ClinicalTrials.gov) and for studies run in the EU/EEA on the EU Clinical Trials Register (www.clinicaltrialsregister.eu) or EU Clinical Trials Portal (https://euclinicaltrials.eu/home). The sponsor also provides clinical trial information to other national clinical trial registries or databases according to local requirements/legislation. A lay language protocol synopsis and a summary of the study will be made available on the EU Clinical Trials Portal (https://euclinicaltrials.eu/home) and/or Sponsor website. 	Minor additions/updates to comply with protocol template guidance.

Section	WAS (Version 2.0, 13 SEPTEMBER 2022)	IS (Version 3.0, 04 DECEMBER 2023)	Rationale
Section 10.1.9 Publication Policy	
 The results of this study may be published or presented at scientific meetings. If this is foreseen, the investigator agrees to submit all manuscripts or abstracts to the sponsor before submission. This allows the sponsor to protect proprietary information and to provide comments. 	
 The sponsor seeks to publish the results of these clinical trials in biomedical journals, whatever the outcome. Clinical trial results may also be presented at international congresses as posters or oral presentations. The results of this study may be published or presented at scientific meetings. If this is foreseen, the investigator should discuss specific publication concepts, including data to be covered, target congress/journal and proposed authors, with the sponsor for agreement before initiation. The investigator agrees to submit all manuscripts or abstracts to the sponsor before submission. This allows the sponsor to protect proprietary information and to provide comments. 	Minor additions/updates to comply with protocol template guidance.
Section 10.3.2 Definition of SAEs	
e. Is a congenital anomaly/birth defect
 
f. Other situations:
 
Medical or scientific judgment should be exercised by the investigator in deciding whether SAE reporting is appropriate in other situations such as significant medical events that may jeopardize the participant or may require medical or surgical intervention to prevent one of the other outcomes listed in the above definition. These events should usually be considered serious.
 
Examples of such events include invasive or malignant cancers, intensive treatment for allergic bronchospasm, blood dyscrasias,
	
e. Is a congenital abnormality/birth defect
 
f. Other situations:
 
Medical or scientific judgment should be exercised by the investigator in deciding whether SAE reporting is appropriate in other situations such as significant medical events that may jeopardize the participant or may require medical or surgical intervention to prevent one of the other outcomes listed in the above definition. These events should usually be considered serious.
 
Examples of such events include invasive or malignant cancers, intensive treatment for allergic bronchospasm, blood dyscrasias,
	Deletion of the statement about the seriousness assessment of COVID-19 adverse events. This means that COVID-19 is no longer to be reported as a serious adverse event unless the occurrence of COVID-19 meets the defined seriousness criteria.

Section	WAS (Version 2.0, 13 SEPTEMBER 2022)	IS (Version 3.0, 04 DECEMBER 2023)	Rationale
	
convulsions or development of intervention dependency or intervention abuse.
 
A suspected or confirmed coronavirus COVID 19 (SARS CoV 2) infection must be reported as serious (seriousness criteria should be “other medically significant” if no other seriousness criteria are present (e.g. hospitalisation).
	
convulsions or development of intervention dependency or intervention abuse.
	
Section 10.3.4 Reporting of SAEs	
 The primary mechanism for reporting an SAE to the sponsor will be the electronic data collection tool. (...) Contacts for SAE reporting can be found on the SAE form and the cover sheet. 
SAE Reporting to the sponsor via paper
 
 Contacts for SAE reporting can be found on the SAE form and the cover sheet. 	
 The primary mechanism for reporting an SAE in English language to the sponsor will be the electronic data collection tool. (...) SAE report should be sent to [contact]. 
SAE Reporting to sponsor via paper data collection tool
 
 SAE report should be sent to [contact]. 	Minor additions/updates to comply with protocol template guidance.
Section 10.5.1.7 Adverse Event Reporting	
As per the protocol (Appendix 10.3.2), all COVID-19 cases (suspected or confirmed) should be considered as SAEs.
 
“Other medically significant” should be selected as seriousness criterium if no other seriousness criteria are present (e.g. hospitalisation).
 
Details can be collected by site staff via telephone call as per the rules relating to use of telemedicine in the protocol (Appendix 10.5.2).
	
All COVID-19 cases (suspected or confirmed) should be seriousness assessed based on the reported seriousness criteria. If no seriousness criteria is reported by the investigator, the COVID-19 event/case will be collected and recorded as nonserious.
 
Details can be collected by site staff via telephone call as per the rules relating to use of telemedicine in the protocol (Appendix 10.5.2).
	Amended for consistency with Section 10.3.2.

Section	WAS (Version 2.0, 13 SEPTEMBER 2022)	IS (Version 3.0, 04 DECEMBER 2023)	Rationale
Section 10.5.2 Specific Rules Related to Use of Telemedicine	Note that further information about measures adopted for the COVID-19 situation to cover SAE reporting and temporary discontinuations are found in Sections 10.3.4 and 7.1.1, respectively.		Amended for consistency with Sections 10.3.2 and 10.5.1.7.

Other documents impacted:

Informed consent form Yes No
Case report form (CRF) Yes No
Statistical analysis plan (SAP) Yes No

TABLE OF CONTENTS

PROTOCOL AMENDMENT SUMMARY OF CHANGES	4
TABLE OF CONTENTS.....	11
LIST OF ABBREVIATIONS.....	15
1 PROTOCOL SUMMARY	16
1.1 Synopsis.....	16
1.2 Schema	19
1.3 Schedule of Activities.....	19
2 INTRODUCTION	23

IRB	Institutional Review Board
IWRS	Interactive Web Response System
LH	Luteinizing hormone
LHRH	Luteinizing hormone releasing hormone
MedDRA	Medical Dictionary for Regulatory Activities
MRI	Magnetic resonance imaging
NCI-CTC	National Cancer Institute – Common Toxicity Criteria
PP	Per protocol
SAE	Serious adverse event
SAP	Statistical analysis plan
SD	Standard deviation
SoA	Schedule of activities
TEAE	Treatment emergent adverse event

1 PROTOCOL SUMMARY

1.1 Synopsis

Protocol Title:

An open-label, multicentre, single arm study to assess the efficacy and safety of triptorelin 6-month formulation administered subcutaneously in participants with locally advanced and/or metastatic prostate cancer previously treated and castrated with a GnRH analogue

Short Title: Effects of triptorelin when given every 6-months under the skin to adult males with cancer in the prostate

Rationale:

Triptorelin is an agonist analogue of natural gonadotropin-releasing hormone (GnRH). The principal modification consists of substitution of natural glycine in position 6 by a D-amino acid (D-tryptophan) leading to improved receptor binding affinity and a longer activity time. The GnRH analogues, of which triptorelin belongs to, are used in the treatment of prostate cancer. Triptorelin is available on the market for more than 30 years under different formulations: 1-month, 3-months and 6-months. Clinical studies have shown that triptorelin 6-month formulation (22.5 mg) administered intramuscularly rapidly induces and maintains castration in patients with locally advanced or metastatic prostate cancer [[Lundström 2009](#), [Breul 2017](#)]. Since 2009, different authorities, including those in Europe, have approved the aforementioned formulation and route of administration which is currently prescribed by many physicians for the treatment of advanced prostate cancer. Although intramuscular injection is mostly used, physicians prefer subcutaneous administration, as this method has less theoretical interactions with some medications patients may take for cardiovascular morbidities. Considering the patient age (elderly), as well as their body mass index (obese versus frail) and co-morbidities (requiring some to take concomitant medications (e.g. oral anticoagulants)), the subcutaneous administration of any injectable is considered more convenient for the patient. Positive outcomes from a previous clinical study performed with the triptorelin 3-month formulation manufactured by Ipsen (already marketed for intramuscular administration) and administered subcutaneously [[Lebret 2015](#)] has led to the registration and commercialisation of this new route of administration in Europe and worldwide.

The present study will assess the efficacy and safety of the 6-month triptorelin formulation (22.5 mg) administered subcutaneously (twice a year) in participants with locally advanced and/or metastatic prostate cancer previously treated and castrated by a GnRH analogue.

Objectives and Endpoints:

Objectives	Endpoints
Primary	

 To evaluate the efficacy of triptorelin embonate 22.5 mg 6-month formulation administered subcutaneously in maintaining serum testosterone castrate levels in participants with advanced prostate cancer previously treated and castrated with a GnRH analogue. 	
 Percentage of participants maintaining castrate levels of serum testosterone during the study (maintenance of castration defined as testosterone <1.735 nmol/L (50 ng/dL) at Day 29, Day 85, Day 141, Day 169, Day 253, Day 309 and Day 337)
Secondary	

 To evaluate the efficacy of triptorelin embonate 22.5 mg 6-month formulation administered subcutaneously on castration 	
 Percentage of participants castrated at each timepoint on Day 29, Day 85, Day 141, Day 169, Day 253, Day 309 and Day 337, (castration defined as testosterone <1.735 nmol/L (50 ng/dL))

 To evaluate the efficacy of triptorelin embonate 22.5 mg 6-month formulation administered subcutaneously on testosterone levels <0.694 nmol/L (20 ng/dL) 	
 Percentage of participants with a serum testosterone level <0.694 nmol/L (20 ng/dL) during the study Percentage of participants with a serum testosterone level <0.694 nmol/L (20 ng/dL) at each timepoint on Day 29, Day 85, Day 141, Day 169, Day 253, Day 309 and Day 337

 To demonstrate the effect of triptorelin embonate 22.5 mg 6-month formulation administered subcutaneously to suppress the 'acute-on-chronic' effect following the administration of the second dose 	
 Percentage of participants castrated, on Day 3 and Day 7 after each injection administered on Day 1 and Day 169 (castration defined as testosterone <1.735 nmol/L (50 ng/dL))

 To demonstrate the effect of triptorelin embonate 22.5 mg 6-month formulation administered subcutaneously in the maintenance of PSA 	
 Percent change in PSA from baseline (prior to injection) at Day 169 and Day 337 (Percent change in PSA defined as the absolute value of difference between the PSA values at Day 169 and Day 337 and the baseline value divided by the baseline value)

 To demonstrate the safety profile of triptorelin embonate 22.5 mg 6-month formulation administered subcutaneously 	
 Incidence of TEAEs (including local tolerability) throughout the study i.e. up to Day 337 Change from baseline in clinical safety laboratory parameters (blood chemistry and haematology) at Day 337 Change from baseline in physical examination at Day 169 and Day 337 Change from baseline in ECG at Day 337 Change from baseline in vital signs (blood pressure and heart rate) at each visit up to Day 337

AE=adverse event; ECG=electrocardiogram; PSA=prostate-specific antigen; TEAE=treatment emergent adverse event

Note: A list of laboratory parameters to be assessed during the study are presented in Appendix 10.2.

The primary estimand for the primary endpoint is described below. The treatment will be triptorelin 6-month formulation administered subcutaneously. The population will comprise participants with locally advanced and/or metastatic prostate cancer previously treated and castrated with a GnRH analogue as specified in the inclusion and exclusion criteria (Sections 5.1 and 5.2), respectively, that have received two scheduled treatment intervention doses (i.e. Day 1 and Day 169) and have completed all visits for measurement of testosterone.

The variable for the primary estimand will be castration maintenance rate during the study, which is defined as percentage of participants castrated (testosterone <1.735 nmol/L (50 ng/dL)) at Day 29, Day 85, Day 141, Day 169, Day 253, Day 309 and Day 337, with two complete study intervention administrations. Secondary estimands include analyses without using the visit window and/or using the ITT population where missing data will be considered a non-responder maybe conducted. Further details of the estimand will be specified in the statistical analysis plan (SAP).

Overall Design:

This is a phase III, multicentre, open-label, non-comparative, repeated dose study to evaluate the efficacy and safety of triptorelin embonate 22.5 mg 6-month formulation administered subcutaneously in participants with locally advanced and/or metastatic prostate cancer previously treated and castrated with a GnRH analogue. Approximately 145 adult male participants will be enrolled in the study. All enrolled participants will receive a subcutaneous injection of triptorelin embonate 22.5 mg 6-month formulation on Day 1 and Day 169.

Note: participants must receive study intervention on Day 1 in accordance with the treatment schedule of their previously received GnRH analogue therapy.

Intervention Groups and Duration:

Triptorelin embonate 22.5 mg (6-month formulation), subcutaneous injection on Day 1 and Day 169.

Visit Frequency:

The study will consist of a Screening period (up to 28 days before enrolment), first open-label injection of the study intervention on Day 1. Following the first treatment, visits will occur on Day 3, Day 7, Day 29, Day 85, Day 141, Day 169 (second injection), Day 171, Day 175, Day 253, Day 309 and Day 337 for efficacy and safety assessments. (Note: if necessary, participants can request home visits, except for visits where study intervention is to be administered).

Participants will receive two injections of triptorelin embonate 22.5 mg (6-month formulation) during the study period before they attend the end of study (EoS) visit on Day 337.

Study Participant Duration:

Participants are expected to participate in this study for 52 weeks, including up to 4 weeks for screening.

Number of Participants:

Approximately 145 participants are planned to be assigned to study intervention.

Statistical Methods:*Sample Size Determination*

This single-arm study is designed to demonstrate that the percentage of participants remaining castrated (maintenance of castration defined as testosterone <1.735 nmol/L (50 ng/dL) at Day 29, Day 85, Day 141, Day 169, Day 253, Day 309 and Day 337) during the study is greater than 90%. Considering an observed castration maintenance in 97% of participants, 130 eligible

participants are required to demonstrate the efficacy of the triptorelin 6-month formulation with approximately 90% power and a one-sided alpha of 0.025 using an exact binomial test. The objective will be achieved if the lower bound of the 95% confidence interval (CI) of the observed rate is greater than 90%.

Considering a drop-out rate of 10%, 145 participants will be included in the study.

Efficacy Analyses

Due to the single-arm nature of the study, all statistical analyses will be descriptive with quantitative data summarised as mean, standard deviation (SD), median, quartiles, 95% CIs and range. Qualitative data will be summarised as frequency counts and percentages. The 95% CIs will be calculated following the Clopper-Pearson method. The descriptive statistics of treatment effects and corresponding 95% CIs for the primary endpoint and secondary endpoints will be presented.

Missing castration level data during the study will be imputed by multiple imputation. Further details of the efficacy analyses will be specified in the SAP.

Safety Analyses

All adverse events, treatment-emergent adverse events and serious adverse events will be summarised and tabulated by system organ class and preferred term, including severity and relationship to test product.

[figure not shown]
Values of laboratory parameters and vital signs at baseline, on treatment and the change from baseline to on-treatment levels will be described.

The Common Terminology Criteria for Adverse Events (CTCAE) (Version 5.0 or higher) classification will be used to classify adverse events (AEs) and laboratory abnormalities. The CTCAE grade by participant will be tabulated and listed.

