5.1 Inclusion Criteria

Participants are eligible to be included in the study only if all of the following criteria apply:

- (1) Participant is male and must be 18 years of age inclusive, at the time of signing the informed consent.
- (2) Participant has histologically or cytologically proven prostate cancer with rising PSA after failed local therapy or metastatic disease, or requiring radiotherapy, and be a candidate for long-term (i.e. >1 year) androgen deprivation therapy.
- (3) Participant requires a GnRH analogue treatment for a minimum of 18 months, of which a minimum of 3 months of GnRH analogue treatment has already been provided prior to screening. (Note: participants must receive study intervention on Day 1 in accordance with the treatment schedule of their previously received GnRH analogue therapy).
- (4) Has serum testosterone levels <1.735 nmol/L (50 ng/dL) at screening.
- (5) Has Eastern Cooperative Oncology Group (ECOG) performance status score of 0 to 1 (see Appendix 10.4).
- (6) Has a life expectancy of >18 months.
- (7) Male participants must agree that, if their partner is at risk of becoming pregnant (although highly unlikely in this study population), they will use an effective method of contraception. The participant must agree to use the contraception during the whole of the study and for 9 months after the last dose of study intervention.
- (8) Capable of giving signed informed consent as described in Appendix 10.1 which includes compliance with the requirements and restrictions listed in the informed consent form (ICF) and in this protocol.

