4 ANALYSIS SETS

Screened Set

The screened set will contain all participants who signed an informed consent for this study. In case of re-screening, the participant will be counted once only in the screened set. The previous site and assigned subject numbers will be collected to link the first and second screening data.

Enrolled Set

The enrolled set will contain all participants who were enrolled to study treatment. A participant will be considered as enrolled if he has signed the informed consent form and is assigned to treatment.

Intent-to-Treat Set

The intent-to-treat (ITT) Set will contain all participants who signed an informed consent form and received at least one administration of study intervention and have a serum testosterone level <1.735 nmol/L (50 ng/dL) on Day 1 (pre-dose measurement).

Full Analysis Set

The full analysis set (FAS) will contain all participants who signed an informed consent form and received two administrations of study intervention and completed all visits for testosterone measurement (Day 29, Day 85, Day 141, Day 169, Day 253, Day 309 and Day 337). Note, a participant will be included in the FAS if his testosterone measurement is ≥ 50 ng/dl before the end of treatment, end of study or withdrawn from study, whichever is earlier.

Per Protocol Set

The per protocol (PP) set will contain all participants from the FAS who did not experience any major protocol deviations that may interfere with efficacy evaluation (refer to section 5.3 for details regarding the management of deviations).

Safety Set

The safety set will contain all participants who receive at least one dose of study intervention.

Associated Procedure / Instruction Reference	319480-SOP
Form Reference	080091-FOR v7.0

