ICE4	Same as primary estimand		
Population-level summary			
	Same as primary estimand	Same as primary estimand	Probability of Castration maintenance at Day 337 based on Kaplan-Meier estimate

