5.7.3.2 Main Secondary Analysis

The same strategies as those for the primary estimand will be used for the main secondary analysis in the FAS, with castration maintenance criteria being replaced with 0.694 nmol/L (20 ng/dL) whenever applicable.

For binary secondary endpoints, including castration maintenance (<50 ng/dL) rate at specific timepoints, castration maintenance (<20 ng/dL) rate during the study, castration maintenance (<20 ng/dL) rate at each timepoint, castration maintenance rate along with the associated 95% exact CI will be provided. For percent change in PSA from baseline at Day 169 and Day 337, descriptive statistics will be provided.

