5.7.3.4 Sensitivity Analysis

For castration maintenance (<20 ng/dL) rate during the study, the Kaplan-Meier estimate at Day 337 using the same strategies as Primary-S3 with castration maintenance criteria replacing with as <20 ng/dL will be provided.

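### The SAP's <20 ng/dL maintenance analyses, above all the Kaplan-Meier estimate, include men who were not below 20 ng/dL before the first injection

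*Protocol*

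**What the plan says.** The protocol's secondary endpoint (1.1 Synopsis, repeated in Section 3) is "Percentage of participants with a serum testosterone level <0.694 nmol/L (20 ng/dL) during the study". It mentions neither maintenance nor the baseline value.

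SAP 5.7.3.2 analyses this endpoint in the FAS under the name "castration maintenance (<20 ng/dL) rate during the study". It reuses the primary strategies "with castration maintenance criteria being replaced with 0.694 nmol/L (20 ng/dL) whenever applicable". SAP 5.7.3.4 adds a sensitivity analysis: "the Kaplan-Meier estimate at Day 337 using the same strategies as Primary-S3 with castration maintenance criteria replacing with as <20 ng/dL will be provided". Primary-S3 (SAP 5.7.2.3) is an ITT analysis, and its summary measure is "Probability of Castration maintenance at Day 337 based on Kaplan-Meier estimate".

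Three conditions decide who is analysed:

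- Eligibility (Protocol 5.1, criterion 4): "Has serum testosterone levels <1.735 nmol/L (50 ng/dL) at screening". The Schedule of Activities has this measured by the local laboratory.
- ITT set (SAP 4): participants must "have a serum testosterone level <1.735 nmol/L (50 ng/dL) on Day 1 (pre-dose measurement".
- FAS (SAP 4): participants who "received two administrations of study intervention and completed all visits for testosterone measurement", with an exception for men with a documented value of 50 ng/dL or more. There is no Day 1 testosterone condition.

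No provision requires a value below 20 ng/dL at any time before dosing. SAP 5.7.3.3 plans no subgroups for secondary endpoints, and the by-timepoint <20 ng/dL endpoint starts at Day 29.

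**The concern.** A maintenance probability describes people who start in the state being maintained. At 50 ng/dL the plan respects this for the Kaplan-Meier analysis: the ITT set requires Day 1 testosterone below 50, and the event is a value at or above 50. At 20 ng/dL the event threshold moves but the entry condition does not. A man at 30 ng/dL before the first injection and still at 30 on Day 29 has lost nothing on the study drug, yet he is counted as a loss of maintenance.

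Every participant has already been treated with another GnRH analogue, so the Day 1 level reflects that earlier treatment. In a single-arm trial the Day 1 value is the only internal reference. At stake is whether the <20 ng/dL maintenance figure can be read as what happens on subcutaneous triptorelin, or whether it mixes in the level that men brought with them. An early fall in the curve could be men who never were below 20, not men who escaped suppression.

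**Working it through.** **Step 1. Match the entry condition to the event threshold.**

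| Analysis | Set | Day 1 condition | Failure threshold | Match? |
|---|---|---|---|---|
| Primary rate | FAS | none | 50 ng/dL or above | screening value only |
| Primary-S3 Kaplan-Meier | ITT | below 50 | 50 or above | yes |
| <20 rate (SAP 5.7.3.2) | FAS | none | 20 or above | no |
| <20 Kaplan-Meier (SAP 5.7.3.4) | ITT | below 50 | 20 or above | no |

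The phrase about replacing the criteria where applicable does not close the gap. It acts on the maintenance criterion, not on the definitions of the analysis sets in SAP 4.

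**Step 2. Follow a man at 30 ng/dL on Day 1.** The endpoint's seven assessed visits start at Day 29.

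- Below 20 at Day 29 and at every later visit: a success.
- Below 20 at Day 29 and later at or above 20: a failure, and a real loss of a level reached on study drug.
- Still at or above 20 at Day 29: a failure in the rate and, in the ITT set, a Kaplan-Meier event at the first assessed visit, although he was never below 20.

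Only the third path reports baseline status as loss.

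**Step 3. The plan's own figures.** It states none for the <20 ng/dL endpoint. Its primary design reproduces. With 130 men, a null rate of 90%, a true rate of 97% and an exact one-sided 0.025 test, 124 successes are needed; the exact alpha is 0.0207 and the power 0.9027, against a stated power of about 90%. Then 130/0.9 = 144.4, rounded up to 145. Nothing in this point changes those figures.

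**Step 4. Size.** All three inputs are assumptions, because the documents give no Day 1 distribution:

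- q = share of men at 20 to 49 ng/dL on Day 1 (5% to 20%);
- s = share of those men below 20 by Day 29 (0 to 1);
- m = maintenance among men who start below 20 or get there by Day 29 (95%).

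Reported rate = (1 − q)·m + q·s·m. Shortfall against m = m·q·(1 − s).

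| q | s = 0 | s = 0.5 | s = 1 |
|---|---|---|---|
| 5% | 0.95 × 0.05 × 1 = 4.75 points | 2.4 | 0 |
| 10% | 0.95 × 0.10 × 1 = 9.5 points | 4.75 | 0 |
| 20% | 0.95 × 0.20 × 1 = 19 points | 9.5 | 0 |

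As counts, with 130 men, q = 10% and s = 0: 13 men start at 20 to 49 and 117 start below 20. Among the 117, 111 succeed: 111/117 = 94.9% (exact 95% CI 89.2 to 98.1). Over everyone it is 111/130 = 85.4% (78.1 to 91.0). Each affected man costs 1/130, about 0.8 points.

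This arithmetic is for a simple proportion. The Kaplan-Meier estimate at Day 337 equals that proportion when nobody is censored earlier. With censoring the figures shift, but the men on the third path still enter as early events.

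**The case against.** The strongest reply is that the protocol endpoint has no fault. It asks what percentage of men are below 20 ng/dL. For that question all treated men are the right denominator, and a man still at or above 20 four weeks after injection is a true failure. This stands in full. A reader might infer that the protocol endpoint is itself biased; the documents do not support that. The fault lies in the SAP's maintenance label and in the Kaplan-Meier estimate built on it.

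Three further limits also stand:

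- A reader might infer that every man at 20 to 49 on Day 1 is counted as a loss, or that his event has already happened at time zero. Day 1 is not an endpoint visit, and a man below 20 from Day 29 onward is a success. If all such men get there (s = 1), the shortfall is zero.
- A reader might infer that the swap dropped a Day 1 condition from the <20 rate. It did not: the FAS has no Day 1 condition at either threshold. The mismatch with the 50 ng/dL analysis concerns the Kaplan-Meier estimate; for the rate, the problem is the name.
- It would be too strong to say that inherited level and loss on treatment cannot be separated. SAP 5.4 summarises and lists central-laboratory baseline testosterone, SAP 5.7.1 lists all efficacy data, and the by-visit percentages are sound when read as levels. What is missing is a planned output that links Day 1 status to the <20 result.

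The consequence is also modest. SAP 5.7.1.1 calls the efficacy analysis descriptive, no success threshold attaches to 20 ng/dL, and any distortion lowers the sponsor's own figure.

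These points narrow the concern but do not remove it. The SAP still plans to publish a maintenance probability for a state that its risk set need not have been in.

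**Conclusion.** The point holds for SAP 5.7.3.2 (the label) and SAP 5.7.3.4 (the Kaplan-Meier estimate). The response threshold was moved to 20 ng/dL while the ITT entry condition stayed at 50 ng/dL. Men at 20 to 49 ng/dL before dosing who remain at or above 20 at an assessed visit are therefore reported as loss of maintenance.

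The size cannot be known from the documents. Under the stated assumptions (5% to 20% of men at 20 to 49 on Day 1, none to all of them below 20 by Day 29, 95% maintenance otherwise) the shortfall is 0 to 19 points. The 19-point end requires that no such man gets below 20 by Day 29, so it is an upper edge of the assumed range, not an expectation. The direction is against the product. The primary endpoint, sample size and alpha are not touched. This is a worthwhile and cheap improvement to a secondary analysis, not a threat to the trial's main conclusion.

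**What to change.** - **SAP 5.7.3.2:** keep the all-participant FAS rate, but describe it as the percentage below 20 ng/dL at all seven visits and drop the word maintenance. Show it also split by central pre-dose Day 1 status (below 20 versus 20 to 49 ng/dL). Because the FAS has no Day 1 condition, give any man at 50 or above on Day 1 his own line.
- **SAP 5.7.3.4:** run the <20 Kaplan-Meier maintenance estimate in ITT men whose central pre-dose Day 1 testosterone is below 20 ng/dL, so that the entry condition matches the event, as it already does at 50 ng/dL.
- **By-timepoint <20 table:** add a Day 1 row.

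Specify this before database lock. Restricting to men below 20 on Day 1 would be expected to raise the maintenance figure, so choosing it after seeing results would look selective.

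The cost is SAP wording and one extra split on a sample already scheduled for every participant. The downside is a smaller denominator and a wider interval for the maintenance figure. In the 10% illustration it falls from 130 to 117.
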